### **Statistical analysis plan**

The significance levels of the tests will be accepted as the P-value of  $<0.05$ . Categorical variables will be presented as percentages and will be compared with Chi-square test. Continuous variables will be expressed as mean  $\pm$  SD. Normality test will be used to test the distribution of continuous variables and variables with normal distribution will be compared with Student t-test and those without normal distribution will be compared with Mann-Whitney U test.

Risk factors for safety and efficacy end-points will be identified using logistic regression analysis. Variables with a p value  $<0.10$  in univariate analysis will be entered into multivariate analysis with stepwise backward elimination method.

The Kaplan-Meier method will be used to compare the probability of freedom from clinical combined end points during long-term follow-up. Intention-to-treat analysis will be performed for follow-up findings.

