## **Study Protocol**

This is a double-blind randomized parallel assignment phase 3 interventional study. Patients with persistent AF with a duration of  $\geq 48$  hours undergoing elective electrical cardioversion (CV) will be randomized to TEE-guided versus anticoagulation-guided groups.

In the anticoagulation group, the patients are planned to receive warfarin for at least 3 weeks with an INR value between 2.0-3.0. Those who were unable to use or have contraindications to warfarin will receive novel oral anticoagulants (NOACs) at the recommended dose instead of warfarin for at least 3 weeks. If left atrial thrombus is detected by TEE, no CV will be performed. Other patients in the both groups will undergo electrical CV. After the CV, all the patients will be given warfarin or NOACs for at least 4 weeks and the decision to continue anticoagulant after this period was made based on patients' CHA2DS2-Vasc-score. Patients with a score of  $\geq 1$  in men and  $\geq 2$  in women will take anticoagulation. All the patients will undergo cranial MRI before and 1 week after CV.

Inclusion criteria includes patients with the age of more than 18 years who are planned to undergo electrical CV without anticoagulation use within 48 hours of randomization.

Exclusion Criteria includes urgent CV, patients who have non-MRI compatible implanted pace-makers or other metal devices, claustrophobia, haematological disorders disabling patients to receive anticoagulant agents, AF secondary to temporary causes, serious rheumatic heart valve disease, hyperthyroidism, history of malignancy, left atrium diameter  $> 55$  mm and ejection fraction  $< 0.25$ .

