## **Outcome Measures**

Efficacy outcome measures: Clinical thromboembolic events including ischemic stroke/transient ischemic attack (TIA), other thromboembolic events or death during 2 years follow-up or acute silent cerebral thromboemboli detected by diffusion MRI at 1 week post-CV.

Safety outcome measures All the bleeding events will be recorded.

Combined outcome measures: Clinical efficacy events or major bleeding during 2 years' follow-up or silent cerebral thromboembolism detected by MRI.

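### The treatment comparison is left unadjusted; prespecifying one analysis adjusted for a pre-randomisation CHA2DS2-VASc score would be a cheap, modest improvement, not the correction of an error

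*Combined protocol and SAP*

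**What the plan says.** The Statistical analysis plan section gives two ways to compare the arms. For binary outcomes, "Categorical variables will be presented as percentages and will be compared with Chi-square test". For follow-up, "The Kaplan-Meier method will be used to compare the probability of freedom from clinical combined end points during long-term follow-up". No covariate, stratification factor or model is attached to either.

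Regression appears once, with a different purpose: "Risk factors for safety and efficacy end-points will be identified using logistic regression analysis". Variables that pass a univariate screen at p<0.10 "in univariate analysis will be entered into multivariate analysis with stepwise backward elimination method". Treatment arm is not named as a term, and no covariate is fixed in advance.

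The Study Protocol section mentions randomisation without stratification. It uses CHA2DS2-VASc once, for the period after at least 4 weeks of treatment following cardioversion: "the decision to continue anticoagulant after this period was made based on patients" and their score. No time of scoring is given. The same section says "If left atrial thrombus is detected by TEE, no CV will be performed".

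**The concern.** The efficacy composite covers stroke or TIA, other thromboembolism, death, and silent emboli on MRI. The protocol itself treats CHA2DS2-VASc as a guide to thromboembolic risk, yet the comparison of the arms does not use it. When a covariate predicts the outcome, adjusting for it narrows the interval for the treatment effect and accounts for chance imbalance in that covariate. With no stratification described, nothing else in the plan is stated to do this.

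The stepwise regression does not fill the gap. Arm could be screened out of it, and the other terms depend on the data. An arm effect read from that model would not be a prespecified estimate. Fixing one adjusted analysis in advance also removes the temptation to report such an effect once the data are known.

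**Working it through.** **No stated figure to reproduce.** The documents give no sample size, power, event rate or effect size. From the plan come only the 0.05 significance level (two-sided assumed) and two randomised arms (1:1 assumed). Everything else below is an assumption, shown as a range.

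**Assumed score.** Values 0 to 6 with weights 0.12, 0.20, 0.22, 0.20, 0.14, 0.08, 0.04 (mean 2.44, SD 1.61), acting log-linearly on the odds of an event.

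**Formula.** For overall risk p and risk q(s) at score s, the share of outcome variance explained is R² = [Σ w(s)q(s)² − p²] / [p(1 − p)]. Adjustment multiplies the variance of the risk difference by about 1 − R². A trial with 80% power unadjusted then has power Φ[(1.960 + 0.842)/√(1 − R²) − 1.960].

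Example, p = 10% and odds ratio 1.4 per point: R² = 0.0293, so 2.802/√0.9707 − 1.960 = 0.884 and Φ(0.884) = 81.2%.

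| Odds ratio per point | c-statistic (about) | R², risk 3% to 20% | Adjusted power (80% unadjusted) |
|---|---|---|---|
| 1.0 | 0.50 | 0% | 80.0% |
| 1.2 | 0.58 | 0.3% to 1.4% | 80.1% to 80.6% |
| 1.4 | 0.65 | 1.0% to 4.9% | 80.4% to 81.9% |
| 1.6 | 0.70–0.71 | 2.1% to 9.2% | 80.8% to 83.6% |
| 2.0 | 0.78 | 4.7% to 17.9% | 81.9% to 87.1% |

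In sample-size terms, 10% v 5% needs [1.960√(2 × 0.075 × 0.925) + 0.842√(0.10 × 0.90 + 0.05 × 0.95)]²/0.05², which rounds up to 435 per arm. With R² = 2% this becomes 435 × 0.98, or 427; with R² = 5% it becomes 435 × 0.95, or 414.

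**Simulation check.** 10% v 5%, 435 per arm, 3000 trials per row; Monte Carlo SE about √(0.8 × 0.2/3000) = 0.7 points. Pearson chi-square is set against the Wald test for arm in a logistic model with the score. The variance ratio is that of the standardised risk difference to the unadjusted one.

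| Odds ratio per point | Chi-square | Adjusted | Variance ratio |
|---|---|---|---|
| 1.0 | 80.6% | 79.8% | 1.00 |
| 1.4 | 80.9% | 81.4% | 0.99 |
| 1.6 | 81.3% | 82.6% | 0.96 |
| 2.0 | 80.6% | 84.4% | 0.90 |

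In the first row the variance ratio of 1.00 shows no loss of precision. The small fall in power goes with comparing a Wald test with a Pearson test.

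**Smaller trials with more events.** With 150 or 200 per arm, control risk 15% or 20%, treatment odds ratio 0.45 and 1.3 or 1.6 per point, an adjusted likelihood-ratio test beat Pearson chi-square by 0.4 points (56.2% to 56.6%) to 3.8 points (60.7% to 64.5%). Part of that is the change of test. Likelihood-ratio against likelihood-ratio, the gain is about 1 point at 1.3 per point and about 2.4 to 3.5 at 1.6. Adjusted Wald against Pearson at 1.3, it is −0.5 to +0.7, which is nothing. Under the null (2000 trials each, Monte Carlo SE about 0.5 points), rejection was 4.8% to 5.5% for chi-square and 4.7% to 6.0% for the adjusted likelihood-ratio test.

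**The case against.** The strongest reply is that nothing here is wrong. An unadjusted comparison of randomised arms is valid, and the null rejection rates above agree. Chance imbalance does not bias the test and is already allowed for in the p-value. Lack of stratification is not a defect in itself. All of this stands, and it is why the point is an optional improvement.

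A second reply concerns the score, and it also stands. A reader might infer that a baseline CHA2DS2-VASc already exists for every patient, so that adjustment is free. The documents do not support that. The only stated use is weeks after cardioversion, and a score taken then could already contain a stroke that occurred in the trial. Patients with thrombus on TEE are not cardioverted, so they are not shown to reach that decision. If scoring took place only there, missing values could depend on arm and would sit badly with the planned intention-to-treat analysis.

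A reader might also assume that the score is strongly prognostic here. The efficacy outcome includes "other thromboembolic events or death during 2 years follow-up or acute silent cerebral thromboemboli detected by diffusion MRI at 1 week post-CV", and the combined outcome adds major bleeding; nothing in the documents shows that the score predicts MRI lesions or bleeding. Because the score also decides who continues anticoagulation, its link with 2-year events may be weaker.

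Finally, few events are not an argument for a larger gain. At 1.4 per point, R² falls from 4.9% at 20% risk to 1.0% at 3% risk.

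These replies limit the size of the benefit. They do not remove the case for a low-cost prespecified analysis.

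**Conclusion.** The point holds as a cheap improvement. The planned comparisons are unadjusted, and the stepwise regression does not supply a prespecified adjusted treatment effect.

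The expected gain is modest and rests entirely on assumed risks and an assumed score effect. It is about 0 to 2 power points for a weak to moderate score, about 4 in the simulated trial with a strong one (2.0 per point), and zero if the score does not predict the outcome. The formula gives up to 7 points in its most favourable corner (2.0 per point with 20% risk), but nothing in the documents supports relying on that combination.

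The absence of a sample-size justification and of a named test to go with Kaplan-Meier are separate and larger gaps, and should be settled first.

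**What to change.** - Record CHA2DS2-VASc before randomisation in all randomised patients, including those later not cardioverted.
- Prespecify, outside the stepwise procedure, one treatment comparison with arm forced in and that score as the single linear covariate.
- For binary outcomes, use logistic regression standardised to a risk difference with 95% CI, which avoids reporting only a conditional odds ratio. For time to first clinical event, use Cox regression.
- Keep the unadjusted chi-square as a supporting analysis, and confine stepwise selection to the exploratory search for risk factors.

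The cost is one added data-collection line and a short change to the analysis plan. With few events the model must stay at one covariate, with penalised likelihood if needed.

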## **MRI**

All the patients will undergo diffusion brain MRI before and 1 week after the CV to detect silent cerebral thromboembolic events.

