## **Follow-up**

All the patients will be seen at the first week, first month and then every 3-month thereafter, and at any time the patient experienced any symptoms for 2 years. Complete physical exam including neurological exam will be performed in all the cases on the follow-up. Clinical thromboembolic events and bleeding events will be recorded.

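### The risk-factor search uses logistic regression on 2-year events from an unlisted set of candidates; a Cox model with a short fixed list would suit these end-points better (minor)

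*Combined protocol and SAP*

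**What the plan says.** The Statistical analysis plan sets the method: "Risk factors for safety and efficacy end-points will be identified using logistic regression analysis". Variables below P<0.10 in "univariate analysis will be entered into multivariate analysis with stepwise backward elimination method". It names no candidate variables, gives no retention threshold for the elimination step (only a general 0.05 significance level), and has no rule for patients followed for less than 2 years.

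Under Outcome Measures, the efficacy outcome joins stroke or TIA with "other thromboembolic events or death during 2 years follow-up or acute silent cerebral thromboemboli detected by diffusion MRI at 1 week post-CV". Under Follow-up, "All the patients will be seen at the first week, first month and then every 3-month thereafter", for 2 years.

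The plan already has a time-to-event method for part of this material: "The Kaplan-Meier method will be used to compare the probability of freedom from clinical combined end points during long-term follow-up". It adds: "Intention-to-treat analysis will be performed for follow-up findings".

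The MRI section says "All the patients will undergo diffusion brain MRI before and 1 week after the CV to detect silent cerebral thromboembolic events", while the Study Protocol section says "If left atrial thrombus is detected by TEE, no CV will be performed". No section says how a patient without the post-cardioversion scan is coded.

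**The concern.** There are three gaps.

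- **Partial follow-up.** A logistic model needs one yes/no result per patient. A patient who leaves event-free at 6 months has none for 2 years. In a plain fit that patient is either counted as event-free or left out, and the plan does not say which. If loss differs between levels of a factor, both choices distort its odds ratio, in opposite directions.
- **Missing MRI by design.** Patients with thrombus on TEE are not cardioverted, so they cannot have a 1-week post-cardioversion scan. Any yes/no outcome that includes the MRI finding is then undefined for them unless they have a clinical event. The scan is absent because of thrombus, which is plausibly related to embolic risk, so this is not ordinary random missingness.
- **Open list.** If the number of candidates is not fixed, neither is the chance of reporting a false factor. Nothing commits the authors to show estimates for eliminated candidates.

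At stake is the reliability of the published risk factors. For the MRI gap, the comparison of the two strategies is also affected.

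**Working it through.** The documents give no sample size, event rate, loss rate or number of candidates, so there is no planned figure to reproduce. Every input below is an assumption: 200 patients, 100 at each level of a factor, 10% two-year risk, constant hazard, and loss times uniform over 0–2 years.

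**1. Partial follow-up**

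Hazard: λ = −ln(0.90)/2 = 0.05268 per year.

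Chance that a lost patient has an event before leaving: 1 − 0.10/(2λ) = 1 − 0.10/0.10536 = 0.0509.

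With a fraction f lost, the observed event proportion is e = (1−f)×0.10 + f×0.0509, and the event-free completers are n = (1−f)×0.90. The true odds ratio is 1.

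*Loss 25% versus 5%*
- e = 0.0877 and 0.0975; n = 0.675 and 0.855.
- Lost coded event-free: (0.0877/0.9123)/(0.0975/0.9025) = 0.89.
- Event-free lost patients dropped: (0.0877/0.675)/(0.0975/0.855) = 1.14.

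*Loss 40% versus 10%*
- e = 0.0804 and 0.0951; n = 0.54 and 0.81.
- Coded event-free: (0.0804/0.9196)/(0.0951/0.9049) = 0.83.
- Dropped: (0.0804/0.54)/(0.0951/0.81) = 1.27.

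*Equal loss of 20%:* a null odds ratio stays at 1.00; a true odds ratio of 1.50 becomes 1.49 (event-free) or 1.50 (dropped).

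*Effect on the test.* With 10 events per 100 at each level, SE(log OR) = √[2×(1/10 + 1/90)] = 0.471. The shifts are 0.25 and 0.28 SE at 25% versus 5%, and 0.39 and 0.50 SE at 40% versus 10%. The two-sided false-positive rate for that factor becomes 5.7% and 5.9%, then 6.8% and 7.9%, instead of 5%.

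*Same data as a rate.* Mean time at risk is 0.10/λ = 1.898 years for a patient not lost and 0.0509/λ = 0.966 years for one who is lost. At 25% versus 5% loss, the levels have 0.0877/1.665 and 0.0975/1.852 events per person-year, both 0.0527, a ratio of 1.00. Censoring at last contact removes this bias, provided that loss is unrelated to risk within each factor level.

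**2. List length and selection**

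Simulated with a 0.10 screen and an assumed 0.05 stay level (6,000 trials for the null candidates):

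| Null candidates | At least one false factor | 1 − 0.95^k |
|---|---|---|
| 2 | 9.6% | 9.8% |
| 10 | 38.7% | 40.1% |
| 15 | 52.8% | 53.7% |

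The rates track plain multiplicity. A fixed Cox model with two null covariates and no selection gave 11.1%, no better than the stepwise 9.6%. With a stay level of 0.10, the rate at 10 null candidates is about 65% (1 − 0.90^10 = 65.1%), so the unstated threshold matters.

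Inflation (2,000 trials, two true factors among 10 candidates, mean 20 events), median estimated odds ratio:

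| True OR | Stepwise, retained | Fixed model, significant terms only | Fixed model, all terms |
|---|---|---|---|
| 1.3 | 1.84 | 1.84 | 1.31 |
| 1.5 | 1.91 | 1.91 | 1.50 |

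The inflation comes from reading only significant terms at low power, whichever model is used.

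**3. Missing MRI**

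No arithmetic is possible, because no thrombus frequency is given. Set side by side, the MRI section promises every patient a scan after cardioversion, while the Study Protocol section withholds cardioversion from some. The efficacy and combined outcomes both include the MRI finding, and the plan compares categorical variables by chi-square. The undefined result therefore enters the between-arm test as well as the risk-factor model.

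**The case against.** The strongest reply is that this is an exploratory, secondary analysis, that its selection steps are stated, and that the bias from loss is negligible unless loss is both heavy and uneven. Nothing in the documents predicts such loss. That stands, and it sets the priority.

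Several stronger readings are tempting but not supported.

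- *That stepwise selection itself creates false factors or inflates effects.* The comparisons above show neither. The gain comes from a shorter list and from reporting every term.
- *That eliminated candidates will be hidden.* The plan runs univariate analyses first and does not say that they will be withheld. Under a 0.05 stay level, a true factor is absent from the final model in 81% (OR 1.3) or 63% (OR 1.5) of simulated trials. With a 0.10 stay level this falls to about 72% and 49%. These figures describe one model table, not the whole report.
- *That logistic regression forces lost patients to be coded event-free or dropped.* Imputation or weighting could be used; the plan mentions neither.
- *That the intention-to-treat sentence is breached.* It sets a population, not a missing-data rule.
- *That only the risk-factor analysis is touched.* This holds for the follow-up and list-length gaps but not for the MRI gap.

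It may also be said that Cox regression is a preference. But the plan already treats the clinical combined end points as event times, so a binary model for the same events discards information that is being collected.

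**Conclusion.** The concern holds as a minor point. For events accruing over 2 years, logistic regression without a rule for partial follow-up is a weaker choice than the time-to-event approach the plan uses elsewhere. Under the assumed 10% risk, the distortion of a null odds ratio runs from almost none (equal loss) to 0.83 or 1.27 (40% versus 10% loss). The false-factor rate depends on an unlisted number of candidates and an unstated stay level: about 10% with two null candidates and 39% with ten at a 0.05 stay level.

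The missing post-cardioversion scan is a structural gap of unknown size that also applies to the randomised comparison of outcomes containing the MRI finding. The absent scans may fall mainly in the TEE-guided arm, but that is an inference from the arm's name; the documents give no numbers by arm.

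**What to change.** 1. For 2-year clinical efficacy events, bleeding and the clinical combined outcome, use Cox regression with censoring at last contact. Treat death as a competing event for bleeding (cause-specific hazard). State the time origin and use the same one for the Kaplan-Meier analysis; the plan gives none, and cardioversion in the anticoagulation group follows at least 3 weeks of treatment.
2. Replace the screen and elimination with a short covariate list fixed in advance and suited to each end-point. Use a penalised (Firth) fit with profile-likelihood intervals if events are few. Report every term with its interval, significant or not, and label the results exploratory.
3. Analyse the 1-week MRI finding separately among patients with a post-cardioversion scan. Report by arm how many have none. State that this subset is defined after randomisation, so the arm term is not a purely randomised contrast. Attach the same caveat to the between-arm chi-square comparison of any outcome that includes the MRI finding, and state how unscanned patients are coded there.

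If logistic regression is kept, the minimum is to state the candidate list, the elimination threshold and both coding rules, and to report all estimates.

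**Cost:** SAP wording and a little more analysis; no new data. Fewer candidates are examined, so an unexpected factor may be missed, and the efficacy composite has no single risk-factor model. Power stays low: in simulation with 200 patients, 20% loss and about 18 events, it was about 40% for a hazard ratio of 1.5 per SD. Intervals will be wide.
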